7.2 Secondary Efficacy Variable Analysis

Secondary endpoints will be analyzed and reported as described below. Endpoint assessments will be tabulated by timepoint and in case of more than 2 timepoints additionally be displayed graphically as time course.

All changes from baseline will be analyzed by descriptive statistics for actual and change to end of treatment or latest week 12 and month 6 and reported using standard summary statistics. P-value will be calculated by using paired t-test for change from baseline. This is applicable for the following secondary endpoints:

- Morning voiding volume over time (from patient diaries, until month 6).

Form Title: Statistical Analysis Plan

SOP Number: [REDACTED]	Current Version Number & Date: 1.0 & 30NOV2023	Previous Version Number & Document Date: 0.6 & 10NOV2023
---------------------------	---	--

- Total number of voids and total voiding volume (daytime and nighttime) over the last 24 hours (from patient diaries, until month 6).

[figure not shown]
All changes from baseline will be analyzed by descriptive statistics for actual and change to end of treatment or latest week 12 and month 6 and reported using standard summary statistics. An ANCOVA model, as described below, will be used for baseline comparisons. This is applicable for the following secondary endpoints:

- Change from baseline to end of treatment or latest to week 12 and to month 6 in Bladder Pain/Interstitial Cystitis Symptom Score (BPIC-SS)
- Change from baseline to end of treatment or latest to week 12 and to month 6 in bladder pain and urinary urgency on Visual Analogue Scale (VAS) scored from 0 to 100.
- Change from baseline to end of treatment or latest to week 12 and to month 6 in quality of life (QoL) on Visual Analogue Scale (VAS) scored from 0 to 100.

The changes from baseline to end of treatment or latest week 12 and month 6 in above listed endpoints will be analyzed by Analysis of Covariance (ANCOVA). For the ANCOVA model, change from baseline will be the dependent variable and baseline will be the covariate. The analysis will be performed by using Proc Mixed. The covariance matrix will be left unstructured and the satterswaite approximation will be used for degrees of freedom.

Adjusted least square mean and the standard error values along with the p-value and the 95% confidence will be presented. Single effect for Week 12 and Month 6 will be derived as contrast from the overall model.

The Proc mixed procedure of SAS will be used to compare the change from baseline for Bladder Pain/Interstitial Cystitis Symptom Score (BPIC-SS) by adjustment of continuous baseline values.

The following secondary endpoints will be analyzed and reported like the analysis method and reporting of the primary endpoint as described above:

- Percent responders at month 6 as indicated by change on the 7-point Patient Global Assessment (PGA) scale using the same responder definition as for the primary endpoint.

Form Title: Statistical Analysis Plan

SOP Number: [REDACTED]	Current Version Number & Date: 1.0 & 30NOV2023	Previous Version Number & Document Date: 0.6 & 10NOV2023
---------------------------	---	--

- Percent responders at the end of treatment or latest at week 12 and at month 6 as indicated by change on the 7-point Patient Global Assessment (PGA) scale using an alternative responder definition (i.e. a responder is defined as a patient who experiences moderate or marked improvement).

The following secondary endpoints will be presented by summary statistics:

- Counts and percentages will be presented for occurrence of flares (documented as adverse events) and descriptive statistics will be presented for additional BPIC-SS (at the time of occurrence) (until month 6) by summary statistics.
- Number and percentage of premature termination of treatment will be presented by using frequency tables.
- Use of concomitant IC/BPS and pain medication count (until month 6) will be presented by using frequency tables.

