7.1.4 Morning Voiding Volume

The morning voiding volume will be measured by the patients at home once a week (preferably in the morning of the treatment day) until end of treatment or latest week 12. One additional measurement will be performed at month 6. The patients will be provided with a

measuring cup and the measured voiding volume will be captured in the diary card. The entries from the diary cards will be transferred into the eCRF by the site staff.

7.1.5 24-hour Urinary Frequency and Voiding Volume

The patients will document each urinary void and the respective volume over a period of 24 hours in the diary at home once a week (preferably starting the day before the treatment day) until end of treatment or latest week 12. One additional documentation will be performed at month 6. The total number of voids and the total voiding volume over the 24-hour period (daytime and nighttime) will be transferred into the eCRF by the site staff.

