5.1 Sample Size Determination

Approximately 74 patients (including approximately 10% dropouts before end of treatment or latest week 12), are planned to be included in this study.

[REDACTED]

[REDACTED]

Form Title: Statistical Analysis Plan

SOP Number: [REDACTED]	Current Version Number & Date: 1.0 & 30NOV2023	Previous Version Number & Document Date: 0.6 & 10NOV2023
---------------------------	---	--

Accounting for approximately 10% dropouts before end of treatment or latest week 12, further 7 patients and a total of 74 patients will be included in this study.

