5.5 Change from Baseline

Value of change from baseline at any post baseline visit will be defined as the difference of the non-missing baseline value to the non-missing post baseline value i.e.

Change from baseline (Δ) = post-baseline value at visit X - baseline value, where both values are non-missing.

Percent change from baseline will be calculated as:

$(\text{Assessment value at post-baseline visit X} - \text{baseline value}) / \text{baseline value} * 100$.

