5.11 Methods for Withdrawals, Missing Data

Subjects who are withdrawn prematurely from the study treatment will be included in all analyses (up to the date of withdrawal), regardless of the duration of treatment. The analysis will be done on observed data only, no imputation will be done for missing values.

5.12 Unscheduled visits and Early termination Visit.

As this is a real-life study, no fix visit schedule is foreseen. Therefore, also unscheduled visits are not applicable.

If the patient terminates early, withdraws or is withdrawn, the reason for early termination/withdrawal will be recorded.

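### The month-6 voiding change rests on a paired t-test of observed pairs, although SAP 7.2 already uses a joint mixed model for BPIC-SS and VAS that would keep patients lost after end of treatment

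*SAP*

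**What the plan says.** **Diary endpoints.** SAP 7.2 gives morning voiding volume, 24-hour number of voids and 24-hour voiding volume descriptive statistics for the change to end of treatment (or week 12) and to month 6. It adds: "P-value will be calculated by using paired t-test for change from baseline". SAP 5.5 defines a change only "where both values are non-missing". SAP 5.11 adds: "The analysis will be done on observed data only, no imputation will be done for missing values".

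**BPIC-SS and VAS.** The same section analyses these with Proc Mixed: change as response, baseline as covariate, and the week-12 and month-6 effects taken as contrasts from one overall model. "The covariance matrix will be left unstructured and the satterswaite approximation will be used for degrees of freedom". The SAP calls this ANCOVA, but it is in effect a repeated-measures mixed model.

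**Diary data.** The diary values are recorded weekly until end of treatment or week 12 (SAP 4.8, note 9). After that there is a single month-6 entry; for the 24-hour record, Protocol 7.1.5 says: "One additional documentation will be performed at month 6".

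**Expected loss.** SAP 5.1: "Accounting for approximately 10% dropouts before end of treatment or latest week 12, further 7 patients and a total of 74 patients will be included". No rate is given for week 12 to month 6.

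**Other provisions for missing data.** SAP 7.1 allows an optional sensitivity analysis, under the primary endpoint only. SAP 7.3 has a conditional subgroup (more than 10 early terminations) limited to patients with end-of-treatment data. Neither addresses loss between end of treatment and month 6 for the diary endpoints.

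**The concern.** The secondary objective is the change in voiding measures up to month 6 in the treated patients. At month 6 the paired t-test answers it only for patients who returned a month-6 diary entry. Its mean is unbiased for all treated patients only if loss is unrelated to outcome. A joint model over both visits uses the end-of-treatment value of a patient whose month-6 value is missing, and so needs only the weaker missing-at-random assumption.

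The SAP accepts that model for BPIC-SS and VAS. The month-6 voiding results may therefore describe a different set of patients from the month-6 symptom scores reported beside them, and no visible text gives a reason. What is at stake is the reported month-6 voiding change and its p-value. SAP 1.0 foresees these analyses going into regulatory submissions, if applicable, and manuscripts.

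**Working it through.** **1. The plan's own figure.** 74 − 7 = 67 before dropouts. 67 × 1.10 = 73.7, rounded up to 74, which reproduces the stated total; 67 / 0.90 = 74.4, rounded up to 75, is one patient away. The only stated loss is thus about 10%, and it falls before end of treatment. The basis of the 67 is blacked out and was not rebuilt.

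**2. Bias of the observed-pair mean.** The documents give no figure, so the inputs below are assumptions.

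- End-of-treatment and month-6 changes are bivariate normal, in SD units, positive meaning improvement, with correlation ρ = 0.5 to 0.7.
- A fraction d of patients is lost before month 6: 10%, 20% or 30%.
- Patients below the end-of-treatment median are lost at RR times the rate of the others, RR = 2 to 4.
- Every patient has an end-of-treatment value.

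Loss in the better half is g = 2d / (1 + RR), and in the poorer half RR × g. The mean of a half-normal is 0.798, so

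bias = ρ × 0.798 × [(1 − g) − (1 − RR·g)] / [(1 − g) + (1 − RR·g)].

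- d = 0.10, RR = 2, ρ = 0.5: g = 0.067, RR·g = 0.133; 0.5 × 0.798 × 0.067 / 1.80 = 0.015.
- d = 0.10, RR = 4, ρ = 0.7: g = 0.04, RR·g = 0.16; 0.7 × 0.798 × 0.12 / 1.80 = 0.037.
- d = 0.20, RR = 2, ρ = 0.5: g = 0.133, RR·g = 0.267; 0.5 × 0.798 × 0.133 / 1.60 = 0.033.
- d = 0.20, RR = 4, ρ = 0.7: g = 0.08, RR·g = 0.32; 0.7 × 0.798 × 0.24 / 1.60 = 0.084.

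**3. Simulation of the same scenarios** (5,000 trials each, N = 67 and 74). The joint estimate is the maximum-likelihood estimate that an unstructured model gives under monotone dropout. The false-positive rate is the upper-tail rate of the t-test when the true change is zero (nominal 2.5%); it was not computed for the joint model.

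| Loss by month 6 | Bias, paired mean (SD) | Bias, joint estimate (SD) | Empirical SE of paired mean (SD) | t-test false positives, upper tail |
|---|---|---|---|---|
| 10% | 0.015 to 0.040 | −0.002 to 0.003 | 0.121 to 0.131 | 3.0 to 4.9% |
| 20% | 0.035 to 0.087 | −0.003 to 0.003 | 0.129 to 0.136 | 4.3 to 9.7% |
| 30% | 0.058 to 0.142 | −0.002 to 0.003 | 0.137 to 0.147 | 6.0 to 17.6% |

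**4. Other loss mechanisms.**

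- Loss unrelated to response (20% loss): bias −0.001 SD for both methods.
- Loss driven by the unseen month-6 value (20% loss, ρ = 0.5, RR = 4): 0.122 SD for the t-test and 0.093 SD for the joint estimate. The model removes (0.122 − 0.093) / 0.122, about a quarter.
- Extreme case, all losses being the worst end-of-treatment responders: bias = ρ × φ(z) / (1 − d), where z is the normal quantile at d. At 10% loss this is ρ × 0.1755 / 0.90, or 0.10 to 0.14 SD.
- Graded selection (odds of loss rising 1.6- to 2.7-fold per SD of worse end-of-treatment change), with an assumed true change of −3 voids and SD 4: 3 to 9% overstatement at 10% loss. That is 0.09 to 0.27 voids, or 0.02 to 0.07 SD, so the size depends on the assumed selection.

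**The case against.** **The unbiased result is partly built in.** The main simulation makes loss depend on the end-of-treatment change and gives the joint model that value for everyone. The planned 10% loss occurs before end of treatment, where such a value may not exist. This stands: the gain is for patients lost after end of treatment, under missing at random.

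**The effect is small at the only stated rate.** At 10% loss and moderate selection, 0.04 SD compares with a standard error of about 0.12 to 0.13 SD. This stands. The 20% and 30% scenarios are assumptions, and so is the direction.

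**The split of methods comes from the protocol.** Protocol 8.3.6 names ANCOVA only for BPIC-SS and VAS and treats the diary endpoints as time courses. This explains the split but does not justify it statistically. A figure is missing from the available text just after the diary bullets in SAP 7.2, so a reason given there cannot be excluded.

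**Stronger readings that the documents do not support:**

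- *That the diary endpoints are the most exposed to loss.* BPIC-SS, PGA and VAS are also single month-6 assessments at the same contact, with the same remote fallback (Protocol 6.4).
- *That the voiding results will favour the device.* Nothing shows that poor responders are lost more often; loss of improved patients would reverse the sign.
- *That lost patients vanish from the voiding analysis.* Those lost after end of treatment stay in the end-of-treatment test and in the earlier time-course summaries. SAP 5.0 already reports observed and missing counts, so a reduced month-6 number would be visible.

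**Conclusion.** The concern holds as a modest, conditional weakness of the month-6 diary analysis. If month-6 loss depends on earlier response, the paired t-test mean is biased: about 0.015-0.04 SD at 10% loss and 0.03-0.09 SD at 20%, assuming ρ of 0.5 to 0.7 and a two- to fourfold difference in loss between poorer and better responders. The bias is towards benefit only if poor responders are lost more often. Under the same assumptions a joint model has essentially none. If loss depends on the unseen month-6 value, both methods are biased and the joint model less so.

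The documents give no loss rate from week 12 to month 6, so the actual size cannot be fixed. These endpoints are secondary, all analyses are exploratory, and the primary endpoint is unaffected. The change is worth making because it is cheap and the SAP already contains the method.

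**What to change.** In SAP 7.2, make the following the main analysis of the three diary endpoints:

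- One Proc Mixed model per endpoint, with end of treatment (or week 12) and month 6 in the same model and visit as a factor.
- Unstructured covariance and Satterthwaite degrees of freedom, as for BPIC-SS and VAS.
- Visit contrasts against baseline, with 95% confidence interval and p-value.
- A fallback covariance structure named in advance in case the model does not converge.
- The paired t-test kept as a supportive observed-case result.

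**Baseline.** Decide in advance whether it is a covariate, as for BPIC-SS and VAS, or a response at a third visit. The diary is dispensed at baseline, and the first instillation may take place at that same visit (Protocol 6.1 and 6.2), so some patients may have no pre-treatment diary value. With baseline as a response, their later values still contribute; with baseline as a covariate, or in the paired test, they are dropped.

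**Visits.** Do not add a fixed week-4 visit. SAP 5.12 foresees no fixed schedule, and treatment duration is at the investigator's discretion (SAP 4.8, note 8).

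**Cost.** A few lines of SAP text and one extra model call per endpoint, with no new data. Protocol 8 lets the SAP modify the planned analyses and asks for an amendment only for major changes to the primary endpoint or its analysis, so none appears to be needed. The SAP should state the missing-at-random assumption and its limit.

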1.0 INTRODUCTION

This Statistical Analysis Plan (SAP) provides a comprehensive and detailed description of strategy and statistical technique to be used to realize the analysis of data for Viatris protocol CYST-SLZ-7001, “Real-world evidence observational study to evaluate performance and safety of intravesical sodium hyaluronate (Cystistat®) in the treatment of patients with interstitial cystitis (IC)/bladder pain syndrome (BPS)”.

The reader of this SAP is encouraged to also read the Clinical Investigation Plan (Protocol) for details on the conduct of this study and the operational aspects of clinical assessments and timing for completing a patient in this study. The purpose of this SAP is to outline the planned analyses to be completed to support the completion of the Clinical Study Report (CSR) for protocol CYST-SLZ-7001. The planned analyses identified in this SAP will be included in regulatory submissions if applicable and/or future manuscripts. In addition, exploratory analyses not necessarily identified in this SAP may be performed to support the clinical development program. Any post-hoc, or unplanned, analyses which are not identified in this SAP and will be performed, will be clearly identified in the respective CSR.

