4.4 Study Subject Group

There is one group of treatment in the study:

All patients will receive commercially available Cystistat according to the instructions for use.

Confidential and Proprietary to MEDA Pharma GmbH (A Viatris Company)

Form Title: Statistical Analysis Plan

SOP Number: [REDACTED]	Current Version Number & Date: 1.0 & 30NOV2023	Previous Version Number & Document Date: 0.6 & 10NOV2023
---------------------------	---	--

Cystistat is a clear colourless solution presented in a 50 mL glass vial containing 40 mg sodium hyaluronate. It is manufactured by Mylan [REDACTED] and distributed by third companies in some countries.

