5.3 Method of Treatment Assignment, Randomization and Blinding

Randomization and blinding are not applicable due to only one treatment group.

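### In a one-group study, the ANCOVA-based CIs and p-values for mean change in VAS and BPIC-SS are conditional on the observed baselines and, for the population mean change, too optimistic unless the follow-up-on-baseline slope is near 1 (taking the LS mean at the sample-mean baseline)

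*SAP*

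**What the plan says.** The study has no comparator: "There is one group of treatment in the study" (SAP 4.4) and "Randomization and blinding are not applicable due to only one treatment group" (SAP 5.3).

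For BPIC-SS and the three VAS scores, SAP 7.2 states "An ANCOVA model, as described below, will be used for baseline comparisons" and specifies the model: "For the ANCOVA model, change from baseline will be the dependent variable and baseline will be the covariate". It is fitted in PROC MIXED with unstructured covariance and Satterthwaite degrees of freedom, and the week-12 and month-6 effects are taken as contrasts. The output is described as "Adjusted least square mean and the standard error values along with the p-value and the 95% confidence will be presented". A later sentence on BPIC-SS repeats that the comparison is made "by adjustment of continuous baseline values".

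For the diary endpoints (morning voiding volume, number of voids, voided volume) the same section uses another method: "P-value will be calculated by using paired t-test for change from baseline".

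The SAP does not give the baseline value at which the LS mean is evaluated. It does not say that the inference is conditional on the observed baselines. Protocol 8.3.6 also names ANCOVA with baseline as covariate for these endpoints.

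**The concern.** In a randomised comparison, baseline adjustment sharpens the difference between groups. Here there is no such difference. The LS mean change is itself compared with zero, and adjustment takes the baseline-related part of the variance out of its SE. That part belongs in the uncertainty if the statement is about patients in general, because another sample would have other baselines and therefore another mean change.

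The p-values and 95% CIs for four patient-reported measures are affected. They may be quoted outside the study report: "The planned analyses identified in this SAP will be included in regulatory submissions if applicable and/or future manuscripts" (SAP 1.0). SAP 7.2 would also produce two sets of change-from-baseline p-values, one from the paired t-test and one from ANCOVA, that answer different questions without saying so.

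**Working it through.** **Inputs from the documents.** One group (SAP 4.4, 5.3). Planned total 74, of which 7 are the dropout allowance (SAP 5.1), so n = 74 − 7 = 67; check: 67 × 1.10 = 73.7, rounded up to 74. The derivation of 67 is redacted. BPIC-SS ranges from 0 to 38 (Protocol 7.1.2), with entry only above 18 (Protocol 4.2.1). VAS ranges from 0 to 100, with no entry threshold.

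**Assumptions.** The documents give no SD or baseline/follow-up correlation. Correlation ρ is taken as 0.3, 0.5 and 0.7, and r = follow-up SD / baseline SD as 0.8, 1 and 1.25. Where millimetres are shown, the VAS SD is 22 mm at both times. Data are complete, and the LS mean is evaluated at the sample-mean baseline.

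**Algebra.** Let b = ρr be the slope of follow-up on baseline. At the sample-mean baseline the LS mean equals the raw mean change.
- ANCOVA variance: SDbase² × r²(1 − ρ²) / n.
- Variance of mean change over repeated samples of patients: the same plus SDbase² × (1 − b)² / n. This is the paired variance, SDbase² × (1 + r² − 2ρr) / n.
- SE ratio, ANCOVA to paired: √[ r²(1 − ρ²) / (1 + r² − 2ρr) ].
- Coverage for the population mean change: P(|T| < 1.997 × SE ratio), T on 65 df.

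The extra term is zero only at b = 1.

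**VAS, by formula.**

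| r | ρ | slope b | r²(1 − ρ²) | (1 − b)² | SE ratio | coverage | paired CI wider by |
|---|---|---|---|---|---|---|---|
| 1 | 0.3 | 0.30 | 0.910 | 0.490 | 0.806 | 88.8% | 24% |
| 1 | 0.5 | 0.50 | 0.750 | 0.250 | 0.866 | 91.2% | 15% |
| 1 | 0.7 | 0.70 | 0.510 | 0.090 | 0.922 | 93.0% | 8% |
| 0.8 | 0.3 | 0.24 | 0.582 | 0.578 | 0.709 | 83.8% | 41% |
| 0.8 | 0.5 | 0.40 | 0.480 | 0.360 | 0.756 | 86.4% | 32% |
| 0.8 | 0.7 | 0.56 | 0.326 | 0.194 | 0.792 | 88.2% | 26% |
| 1.25 | 0.3 | 0.375 | 1.422 | 0.391 | 0.886 | 91.8% | 13% |
| 1.25 | 0.5 | 0.625 | 1.172 | 0.141 | 0.945 | 93.6% | 6% |
| 1.25 | 0.7 | 0.875 | 0.797 | 0.016 | 0.990 | 94.8% | 1% |

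**In millimetres** (r = 1, ρ = 0.3, √67 = 8.185):
- ANCOVA half-width: 1.997 × 22 × √0.91 / 8.185 = 5.1.
- Paired half-width: 1.997 × 22 × √1.40 / 8.185 = 6.3.
- At ρ = 0.5 and 0.7 the pairs are 4.6 against 5.4 and 3.8 against 4.2.

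**Simulation checks at n = 67.**
- With equal SDs and 40,000 trials, ANCOVA coverage was 88.9 / 91.3 / 92.9% and paired coverage 94.9-95.1%.
- The two-sided test of no mean change therefore rejects about 11 / 9 / 7% of the time when the true change is zero.
- Bounding VAS at 0-100 gave 88.8 / 91.4 / 93.1%.
- A two-visit model with unstructured covariance gave 88.6-89.6 / 91.0-91.6 / 92.5-92.8%.
- With the baselines held fixed, ANCOVA coverage was 95.0%, so the shortfall comes entirely from the omitted term.

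**BPIC-SS.** The entry cut narrows the baseline spread while follow-up scores are not cut, which raises r and brings the slope nearer 1. Integer scores were simulated from a normal baseline (mean 20-28, SD 5-8 before the cut), kept at 19-38, with follow-up limited to 0-38. By correlation before the cut, coverage was:
- ρ = 0.3: 89.7-92.8%
- ρ = 0.5: 91.8-93.8%
- ρ = 0.7: 93.4-94.5%

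With larger follow-up SDs (7.1-7.8 against a baseline SD of 4.6) coverage was 93.5-94.8%. The lowest value arises when the cut removes little (mean 27, SD 5, ρ = 0.3), where the paired CI is about 19% wider. If r = 1, the VAS rows apply to BPIC-SS at the same observed correlation.

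**The case against.** The strongest reply is that the SAP promises an adjusted LS mean from a regression, and inference conditional on covariates is ordinary practice. For that target the interval has its nominal coverage, and no section names the unconditional population mean change as the estimand. This stands as far as it goes. A reader might infer that the planned CI is simply invalid, or that adjusting for baseline is a mistake; the documents support neither. Conditionally the CI is correct, and the covariate helps the month-6 estimate when visits are missing. What remains is that the SAP never labels the inference as conditional, while SAP 4.6 gives the purpose as demonstrating the device's benefit/risk profile, which readers will take as a statement about patients in general.

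Second, the size rests on assumed SDs and correlations, so the shortfall could be negligible (94.8%) or large (84%). That also stands: 89-93% is only the equal-SD case, and a smaller BPIC-SS shortfall depends on the follow-up SD exceeding the truncated baseline SD.

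Third, the practical effect is modest. Under equal SDs the VAS half-widths differ by 1.2 mm or less, the analyses are exploratory with no decision rule on these endpoints, and the tabulated SD of change lets a reader rebuild the paired CI. This lowers the priority. It does not make the printed interval a 95% interval for the population mean change, and the printed interval is the one likely to be quoted.

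Finally, ANCOVA is in the protocol. Protocol 8 lets the SAP modify its plans, and adding a paired CI leaves the ANCOVA in place.

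**Conclusion.** The concern holds as an unlabelled inference target with an SE that is too small for the natural reading. Provided the LS mean is taken at the sample-mean baseline, the CIs and p-values for VAS and BPIC-SS are too optimistic about the population mean change unless the slope is near 1. The ranges are about 89-93% coverage for VAS with equal SDs, 84-95% across SD ratios 0.8 to 1.25, and about 90-95% for BPIC-SS where the follow-up SD exceeds the baseline SD. The algebra is certain; every SD and correlation is assumed, with n=67 and complete data. The effect of missing month-6 visits was not quantified.

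A reader might go further and conclude that the estimated changes are biased or that the primary result is affected. Neither follows: with complete data the LS mean equals the raw mean change, and the primary responder rate does not use this model. The point is worth correcting because it is cheap, but it does not threaten the study's main conclusion.

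**What to change.** For VAS and BPIC-SS, report the paired 95% CI and p-value for mean change at end of treatment/week 12 and at month 6, using the paired method that SAP 7.2 already applies to the diary endpoints. State the baseline value at which the LS mean is evaluated, and label the ANCOVA CI as conditional on the observed baselines.

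Alternatively, model baseline, week-12 and month-6 values jointly as outcomes in PROC MIXED, with visit as a categorical factor and unstructured covariance, and report visit-minus-baseline contrasts. With complete data this gives the paired SE (in one simulated data set the two agreed exactly), and it still uses every observed visit.

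The cost is SAP wording and a few lines of code. Protocol 8 asks for an amendment only for major changes to the primary endpoint or its analysis, so none should be needed. CIs become about 8-24% wider for VAS with equal SDs and about 0-20% wider for BPIC-SS where its follow-up SD exceeds its baseline SD, with little change where the slope is near 1.
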